8.1.4 Unanticipated Problems Involving Risk to Subjects or Others

Unanticipated problems involving risk to subjects or others are:

- Any serious event (including on-site and off-site adverse events, injuries, side effects, deaths or other problems) which in the opinion of the local investigator was unanticipated, involved risk to subjects or others, and was possibly related to the research procedures.
- Any serious accidental or unintentional change to the IRB-approved protocol that involves risk or has the potential to recur.
- Any deviation from the protocol taken without prior IRB review to eliminate apparent immediate hazard to a research subject.
- Any breach in confidentiality that may involve risk to the subject or others.
- Any other serious and possibly related event which in the opinion of the investigator constitutes an unanticipated risk.

8.2 Adverse Event Follow-up

Adverse events and Serious Adverse Events will be followed up until their resolution or until a stable outcome has emerged.

8.2.1 Pregnancy

Every effort must be made to avoid pregnancy during the study. If pregnancy does occur, Eirion Therapeutics must be informed immediately. The mother and fetus must be followed until the birth of the infant. In general, the follow up will include the course, duration, and outcome of the pregnancy, and the infant outcome. As the investigational product is applied only once during the study, subjects having a positive urine pregnancy test at or after the Week 4 Visit will be permitted to remain in the study.

Medically accepted methods of birth control are surgical sterilization (tubal sterilization or hysterectomy), vaginal ring contraceptive, patch contraceptive, injectable contraceptive, implantable contraceptive, Intrauterine Device (IUD), diaphragm, condom, or spermicidal gel or foam. Oral contraceptives (prescribed birth control pill) are also acceptable provided this method has been used for at least 4 months prior to the qualifying visit with no change of the brand within this period.

9 STATISTICAL PLAN

9.1 Subject Population(s) for Analysis

9.1.1 Sample size

This study is powered based on the interim results of studies LCL-206 and 207.

9.1.2 ITT and PP population

Statistical analysis of efficacy will be performed on the ITT population of all treated subjects with at least one post-baseline visit, including those for whom only incomplete data are available.

Where data are missing due to subject discontinuation or other reasons, the last post-baseline observation carried forward (LOCF) procedure will be used for each post-baseline visit with missing data. The exception to this procedure will be the treatment of missing data only on one side of the face, as discussed below. Subjects who are lost to follow-up and who do not have at least one post-baseline visit will not be included in the analysis.

An additional analysis may be performed in the per protocol population. Subjects will be considered “per protocol” if they complete the final visit evaluation without a major protocol violation. No data imputations will be made for this analysis.

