5.2 Exclusion Criteria

- history of adverse reactions to any prior botulinum toxin treatments
- history of vaccination with botulinum toxin
- history of non-response to any prior botulinum toxin treatments
- botulinum toxin treatment in the prior 6 months
- history of periocular surgery, brow lift or related procedures
- soft tissue augmentation or any procedures affecting the lateral canthal region in the prior 12 months
- dermabrasion or laser treatment in the periocular region in the last 6 months
- topical prescription-strength retinoids in the prior 3 months to the treatment area
- application of any topical prescription medication to the treatment area within 14 days prior to treatment
- subjects on clinically significant, concomitant drug therapy (See section 5.3 below).
- present or history of neuromuscular disease, eyelid ptosis, muscle weakness or paralysis
- present or history of “dry eye”
- systemic aminoglycoside use in the week prior to treatment application
- participation in another investigational drug trial or receiving any investigational treatment(s) within 30 days of Baseline
- alcohol or drug abuse within the past 3 years
- female subjects who are pregnant or are nursing a child
- psychiatric disease interfering with the subject’s ability to give informed consent
- refusal or inability to comply with the requirements of the protocol for any reason

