7.2 Duration of Study

Subject enrollment will take approximately one month. The total study duration will be approximately 7-8 months.

Each subject will participate for up to 26 weeks. There will be a (Qualifying) Baseline Visit on Week 0 and seven in-office visits at Week 1, 2, 4, 8, 12, 18, and 26.

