7.3 Stopping Rules

The study is designed as a sequential, overlapping cohort, dose-escalation trial. Enrollment will be halted after each cohort until a safety review has been completed.

- Enrollment will be halted in the event that one serious adverse event (SAE), considered to be probably or definitely related to the administration of study medication, is observed.
- Enrollment will be halted in the event that one AE is observed considered to be indicative of distant spread of study medication or unintended exposure to other beings.
- The Sponsor may stop the study in its entirety or discontinue individual study centers at its discretion for any reason or, e.g. if it is observed that the protocol or sound clinical practices are not being followed, or for any other reasons.

The study protocol calls for only one single application of study medication at Baseline (Week 0). Since there is no continuous treatment, no stopping rules for subjects are

applicable and subjects will be encouraged to participate in the study until the scheduled termination visit at Week 26.

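### LOCF as the only missing-data rule after a single application can overstate late response if the effect wanes, and can slightly dilute Week 4 if response is still rising

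*Combined protocol and SAP*

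**What the plan says.** Section 9.1.2 bases efficacy on the "ITT population of all treated subjects with at least one post-baseline visit, including those for whom only incomplete data are available". For gaps it says that "the last post-baseline observation carried forward (LOCF) procedure will be used for each post-baseline visit with missing data", and the scope is wide: "Where data are missing due to subject discontinuation or other reasons". The only exception is a score missing on one side of the face, where Section 9.2.2 uses the other side.

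Section 7.3 confirms that study medication is applied once, at Week 0. Section 7.2 then schedules "seven in-office visits at Week 1, 2, 4, 8, 12, 18, and 26". Section 9.2.2 tests the primary endpoint, a reduction of at least 2 points in IGA-C, at each visit by chi-square and names no single primary visit. Section 9.2.3 uses the same population for the composite, SSA and mean-change analyses.

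The only analysis without imputation is optional: "An additional analysis may be performed in the per protocol population". It is limited to subjects who complete the final visit without a major violation. No other missing-data sensitivity analysis is described.

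The documents do not state when the effect of ET-01 starts, peaks or ends, what response rates are expected, or how many subjects are expected to leave. Section 9.1.1 refers only to interim results of two other studies.

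**The concern.** LOCF fills each gap on the assumption that nothing changes after last contact. That is hard to defend when one application is followed for 26 weeks and the purpose of testing at each visit is to trace response over time. An active-arm subject who is a responder at Week 4 or 8 and then leaves is counted as a responder at Weeks 12, 18 and 26. If the effect has worn off by then, the late comparison is biased toward active drug, and the bias looks like duration of effect. Because every visit carries a primary test, this enters the primary analysis.

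The reverse can happen early. If response is still rising, a Week 1 or Week 2 score carried to a missed Week 4 visit understates the Week 4 difference.

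The optional per-protocol analysis cannot show what dropouts do to the result, because it leaves them out.

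**Working it through.** **Inputs from the documents.** 24 subjects on vehicle, 24 at 690 U and 24 at 1,100 U (Section 3.2); chi-square, two-sided 0.05 (Section 9.2.2). There is no stated power or response rate to reproduce.

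**Assumed inputs.** Peak response 40% active and 5% vehicle (active peak varied from 30% to 60%); dropout *d* from 5% to 30%, equal in both arms and unrelated to response; all dropouts leave at the peak; true late response the same in both arms, either 0% or 5%.

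**Late visit.** LOCF rate = (1 − d) × true late rate + d × rate at the carried visit. The true late rate cancels between arms, so false difference = d × (0.40 − 0.05) = 0.35d. For example, at d = 0.10 and true late rate 5%, active is 0.90 × 0.05 + 0.10 × 0.40 = 8.5% and vehicle stays at 5%, a difference of 3.5 points.

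The probability that one chi-square test (24 vs 24, no continuity correction) rejects was obtained by exact enumeration of both binomials:

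| Dropout | False difference (points) | Rejection, true late 0% | Rejection, true late 5% |
|---|---|---|---|
| 0% | 0 | 0% | 1.8% |
| 5% | 1.75 | 0.1% | 2.9% |
| 10% | 3.5 | 1.3% | 5.0% |
| 15% | 5.25 | 4.4% | 8.1% |
| 20% | 7.0 | 9.7% | 11.9% |
| 30% | 10.5 | 24.1% | 21.7% |

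Over active peaks of 30% to 60%, rejection runs from 0.5% to 8.6% at 10% dropout and from 4.2% to 26.6% at 20%.

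A few subjects can matter. One carried-forward responder adds 1/24 = 4.2 points. With no vehicle responders, 4 active responders give p < 0.05; with 1 vehicle responder, 6 are needed.

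**Week 4, if response is still rising.** Assume true Week 4 response of 40% and 5%, and a carried Week 1 rate of 5% in both arms. The difference under LOCF is (1 − d) × 35 points:

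| Missing at Week 4 | Difference under LOCF (points) | Power, LOCF | Power, observed data (n per arm) |
|---|---|---|---|
| 0% | 35 | 89.3% | 89.3% (24) |
| 5% | 33.25 | 86.7% | 87.7% (23) |
| 10% | 31.5 | 83.7% | 86.0% (22) |
| 20% | 28.0 | 76.4% | 79.6% (19) |

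Beyond what the missing data cost anyway, LOCF loses about 1 to 3 points of power.

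**Check of the simplest alternative.** Counting missing as non-response removes the late false difference when dropout is equal. At Week 4 with 10% missing it gives 0.90 × 40% − 0.90 × 5% = 36.0% − 4.5% = 31.5 points, the same as LOCF. It therefore does not repair Week 4, and it shrinks the difference at any peak visit by 0.35d.

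**The case against.** The strongest reply is that the harm depends on facts the documents do not supply. A reader might take the exclusion for "botulinum toxin treatment in the prior 6 months" as proof that the protocol expects the effect of ET-01 to be gone by Week 26. It is an eligibility washout for any earlier botulinum treatment. It supports waning by about six months only indirectly and says nothing about Week 12 or Week 18. A reader might also infer that a Week 1 or Week 2 score precedes the onset of effect; nothing in the documents supports that. Both objections stand, so the point has to be conditional.

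Who leaves also matters. If non-responders leave, or subjects leave after the effect has gone, LOCF carries non-response forward and creates no false late efficacy. If the drug never works and dropout is equal and unrelated to response, there is no bias between arms. This stands too.

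There are mitigations. Section 5.4 encourages early leavers to complete the Week 26/End of Study procedures, and Section 7.3 encourages subjects to stay to Week 26. This may reduce late gaps but does not secure a Week 26 IGA-C score: Section 6.1.9 ties exit procedures to the visit at which the subject leaves, and the End of Study column in Section 3.5 lists only laboratory and antibody tests. Section 9.5 provides for an SAP before unblinding, which could add analyses, but none is specified now.

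None of this gives a reason to expect a constant score, which LOCF needs.

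**Conclusion.** The concern holds in conditional form. LOCF is the sole rule for efficacy gaps in the ITT analyses to Week 26, and no planned analysis shows how far the results depend on it. If the effect wanes and active subjects leave while responding, late response is overstated by about 3.5 points at 10% dropout and 7 points at 20%, under the assumed 40% vs 5% peak. At 5-10% dropout the main harm is an inflated late rate and apparent duration. With that peak, false significance in a single test clearly passes 5% only from roughly 15-20% dropout; a higher peak lowers that threshold. The Week 4 effect is small and arises only if response is still rising.

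The documents do not support the stronger statement that dropouts will create false late efficacy in this trial. Every response and dropout rate above is an assumption.

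A minor separate point is that the set labelled ITT leaves out some treated subjects: "Subjects who are lost to follow-up and who do not have at least one post-baseline visit will not be included in the analysis". The plan defines this openly, and the documents give no basis for its size or direction. A label that says so would be enough.

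**What to change.** In Sections 9.1.2 and 9.2.3, replace LOCF as the main rule:

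- **Mean change (IGA and SSA):** a repeated-measures mixed model with treatment, visit, treatment-by-visit and baseline, fitted to observed data without imputation.
- **Responder status at each visit:** multiple imputation based on the observed scores over time, with response then derived from the imputed scores and results combined across imputations.
- **Sensitivity analyses:** missing counted as non-response, and LOCF. Missing-as-non-response should not be the main rule, because it dilutes Week 4 as LOCF does and shrinks the difference at peak visits.

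The cost is SAP wording, somewhat more programming, and modelling assumptions in a small sample. Both main methods assume that, given the observed scores, missingness does not depend on the unseen ones. With 24 per arm the imputation model has to stay simple. No change to visits or data collection is needed, and Section 9.5 already allows such changes to be described and justified before unblinding.

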9.2 Statistical Methods

9.2.1 Study Population

Descriptive statistics will be used to summarize demographic characteristics (age, gender, race, height and weight) and background characteristics for all randomized subjects by treatment group. Past/coexistent medical history information for all randomized subjects will be presented in a by-subject listing. Baseline assessments of LCL severity will also be presented as background characteristics of the population and summarized by treatment group.

Demographic data will be summarized using descriptive statistics. Categorical measures will be summarized by counts and percentages. Continuous measures will be summarized with means, standard deviations and ranges (min and max).

Descriptive statistics will be used to summarize study medication compliance and exposure for all randomized subjects. Prior and concomitant medication information for all enrolled subjects will be presented in a by-subject listing.

9.2.2 Primary Efficacy Analysis

The IGA and SSA scores (Crow’s Feet Wrinkle scale) are evaluations performed by the investigator and the subject, respectively, measured both at rest and on contraction. For analysis purposes they will be averaged between left and right sides prior to analysis. In the event one side has missing data for a visit, the result from the side with non-missing data will be used instead of an average value. These scores will be treated as continuous measures for calculating means and performing ANOVA analyses, and they will be used as described below to derive binary indicators of treatment success, which will be analyzed as dichotomous measures.

Efficacy analyses will be based on the assessments from the treatment areas, i.e. the lateral canthal area only. Alpha will be set at 0.05 using two-tailed tests. The Crow’s Feet Wrinkle scale is an ordinal categorical scale ranging from 0 to 4. As described above, left- and right-side values will be averaged, and the averaged values will be used for analysis.

The Investigator’s Global Assessment (IGA) is the primary efficacy parameter, and the evaluation of each active drug group vs. vehicle will be the primary comparisons. A comparison between the two active drug groups will also be performed, along with a

comparison between the two active drug groups pooled vs vehicle. Results will be summarized for each treatment group and at each visit using frequency distributions.

For the primary efficacy analysis, "IGA on contraction" (IGA-C) data will be analyzed at each visit to evaluate the proportion of patients achieving treatment success (responder). For this analysis, a response will be defined as a reduction from baseline in IGA-C by at least 2 points. A separate chi-square test will be used to evaluate the effect of each dose of ET-01 compared to Vehicle. A chi-square test will also be performed evaluating the overall effect of active drug vs vehicle by collapsing the two active drug treatment groups for this analysis. In addition, a separate chi-square test will be used to compare the two active drug groups. The ITT population will be used for this analysis.

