9.2.5 Interim Analysis

Interim analyses for efficacy and safety may be conducted after all subjects have passed the Week 4 visit. As there is only one treatment at Baseline and, therefore, interim analyses will not alter the conduct of the trial, no alpha adjustment will be required.

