9.3 Significance

Unless otherwise specified, all statistical tests will be conducted against a two-sided alternative hypothesis, employing a significance level of 0.05.

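### The primary responder test is run for two doses at seven visits, each at 0.05, with no primary visit or multiplicity rule, so 0.05 holds per test but not for the primary analysis as a whole

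*Combined protocol and SAP*

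**What the plan says.** Section 9.2.2 sets the level ("Alpha will be set at 0.05 using two-tailed tests") and names the contrasts of interest: "the evaluation of each active drug group vs. vehicle will be the primary comparisons". The primary variable is response on IGA-C, defined as a fall of at least 2 points from baseline. On timing, the section says that "data will be analyzed at each visit to evaluate the proportion of patients achieving treatment success (responder"). On method: "A separate chi-square test will be used to evaluate the effect of each dose of ET-01 compared to Vehicle". Pooled active against vehicle and dose against dose are further chi-square tests in the same section.

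Section 7.2 gives the post-baseline schedule as "seven in-office visits at Week 1, 2, 4, 8, 12, 18, and 26", which agrees with the visit table in 3.5. Section 9.3 sets the default for the whole plan: "all statistical tests will be conducted against a two-sided alternative hypothesis, employing a significance level of 0.05".

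No section names a primary visit, orders the two doses, or adjusts the primary tests. Adjustment is waived explicitly in only two places: the secondary ANOVA contrasts (9.2.3) and the optional interim (9.2.5). For the primary tests the plan is silent, so the per-test default in 9.3 applies. Section 9.5 promises a separate SAP before the study is completed and the database unblinded.

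**The concern.** A primary analysis should have one answer. As written, this one has 14, and any of them could be reported as a positive primary result at the 5% level. Which visit matters most can be decided after the results are known.

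The interim provision adds to this. Section 9.2.5 says: "Interim analyses for efficacy and safety may be conducted after all subjects have passed the Week 4 visit". It waives adjustment because the conduct of the trial will not change. That reasoning does not cover the choice of which visit to emphasise once efficacy by arm has been seen and the later visits are still to come. Section 9.5 does not say that the SAP must be final before such an interim.

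**Working it through.** **Inputs from the documents.** Two primary comparisons (9.2.2); seven post-baseline visits (3.5, 7.2); two-sided 0.05 per test (9.2.2, 9.3); arms of 24, 24 and 24 with vehicle pooled over the two cohorts (3.2); uncorrected 2x2 chi-square (9.2.2).

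**Inputs not in the documents, assumed.** The null response rate and the correlation between visits. Section 9.1.1 says only that the study is powered from interim results of two other studies and gives no rates.

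**1. The plan's own figure.** One dose at one visit has a nominal level of 0.05. That reproduces.

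**2. Number of primary tests.** 2 doses x 7 visits = 14. Expected false positives if all nulls are true: 14 x 0.05 = 0.7.

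**3. Reference points.** If the tests were independent, 1 - 0.95^14 = 0.512. The upper bound is 14 x 0.05 = 0.70. Neither is realistic, because the same subjects are scored repeatedly and both doses share one vehicle group. The shared group alone gives a correlation of 24/(24 + 24) = 0.5 between the two dose statistics.

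**4. Large-sample calculation with correlation.** With that 0.5, and correlation between visits of the test statistics of 0.5 / 0.7 / 0.9, the chance of at least one significant result is 0.38 / 0.30 / 0.20 (exchangeable) or 0.44 / 0.38 / 0.25 (AR(1)).

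**5. Simulation of the actual test.** 24 per arm, exchangeable latent correlation 0.5 to 0.9, 20,000 trials per setting:

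| Assumed null response | Any of 14 significant | Any favouring ET-01 |
|---|---|---|
| 10-30% | 31-47% | 15-24% |
| 5% | 14-20% | 7-11% |
| 3% | 4-6% | 2-3% |
| 2% | 1-2% | about 1% |
| 1% | 0.1-0.2% | about 0.1% |

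These ranges are good to about a percentage point. If the null rate instead varies over the visits, peaking at 20% and ending at 2%, the any-significant figure is 28-36%. With a peak of 10% it is 18-21%.

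**6. Why the problem fades at low rates.** With no responders among 24 on vehicle, 3 of 24 on active gives chi-square = 0.125^2 / (0.0625 x 0.9375 x 2/24) = 3.20, below 3.84. It takes 4 of 24: 0.1667^2 / (0.0833 x 0.9167 x 2/24) = 4.36. When response is rare, that many responders seldom occurs by chance.

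**7. What a remedy achieves.**
- One visit, both doses at 0.05: 1 - 0.95^2 = 0.0975 if independent, and 0.091 with the shared vehicle group. Simulated values are 0.086-0.097 at 10-30% null response and 0.034 at 5%.
- One visit, 0.025 per dose: 0.046 with the shared vehicle group.
- One visit, fixed sequence at 0.05: 0.05.
- All seven visits kept as primary: Bonferroni needs 0.05/14 = 0.0036 per test.

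**The case against.** **The plan never claims a family-wise 5%.** A reader might infer that a stated overall alpha is being broken. The documents do not support that: 9.3 attaches 0.05 to each test, and no section calls it an overall level. This stands. The point is that the declared primary analysis has no overall level at all.

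**The size depends on an unknown rate.** A fall of 2 points in a left-right average, from an entry score of 3 to 4 on contraction (5.1), could be rare on vehicle. At 3% or below the inflation essentially disappears. This also stands, and it makes the magnitude conditional. It does not supply a primary visit or a decision rule.

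**Only errors favouring ET-01 could be presented as success.** That is correct, and it is roughly half of the two-sided figure.

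**Larger counts are tempting.** Adding the pooled and dose-against-dose tests gives 4 x 7 = 28, and the at-rest repeat would double that. But 9.2.2 reserves the primary label for each dose against vehicle, and the at-rest analyses are under secondary analyses (9.2.3). Those tests do not belong in a statement about the primary error rate. Nor should 51% be read as the likely figure, since it needs independent tests.

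**This is a small Phase 2 trial and a SAP is promised.** Both facts lower the severity. The SAP could legitimately hold the rule, and the plan could instead declare all efficacy testing exploratory. It currently does neither: it names a primary analysis, fixes an alpha and calls the study powered.

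**Conclusion.** The concern holds in this form: 14 tests carry the primary label, each at 0.05, and nothing ties them to a single conclusion. At an assumed null response of 10-30% the chance of at least one false significant primary test is about 31-47%, of which 15-24% is the chance of one favouring ET-01. At 5% the figures are 14-20% and 7-11%. At 3% or less the overall figure is about 5% or lower. All of these rest on 24 per arm, a shared vehicle group and latent between-visit correlation of 0.5 to 0.9. LOCF (9.1.2) would tend to push that correlation up, towards the lower end of each range.

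A reader might also take Week 4 as the implied primary time point. The documents do not fix it: the interim in 9.2.5 is optional, and the Week 4 step that 3.1 requires before the next cohort is a safety review.

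Severity: should fix. The trial is a 72-subject Phase 2 study and the remedy is text only.

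**What to change.** - **9.2.2, visit.** Name one primary visit, chosen by the sponsor. Week 4 is one option among the seven.
- **9.2.2, doses.** Control alpha across the two dose-against-vehicle tests at that visit. Bonferroni or Holm, starting at 0.025 per dose, does this and still works if only one active group is enrolled. A fixed sequence at 0.05 also works, but it must state what happens if the second cohort is not enrolled, since 3.1 and 7.3 allow enrollment to stop after the first. A sequence starting with 1,100 U would otherwise leave 690 U without a formal test.
- **9.2.2 and 9.2.3, remaining tests.** Label all other visits and the pooled, dose-against-dose and at-rest tests as supportive, with nominal p-values.
- **9.5.** Require the SAP to be final before any efficacy analysis by arm, including the optional interim in 9.2.5.

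If no formal claim is intended, stating that all efficacy tests are exploratory would also settle the point.

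**Cost.** Wording only, with no added subjects or procedures. Other visits could no longer be claimed as primary successes, and under Bonferroni each dose faces a stricter level. For illustration, with assumed response of 10% on vehicle and 40% on active at 24 per arm, exact power is 0.71 at 0.05 and 0.60 at 0.025. For 5% against 40% it is 0.89 and 0.82. Keeping all 14 tests primary under Bonferroni would cut these to 0.30 and 0.51, which is why naming one visit is the cheaper route.

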3 STUDY DESIGN

3.1 Overall Design

The study will be an out-patient, prospectively randomized, double-blind, vehicle-controlled, two-armed, overlapping, sequential ascending dose group, multi-center clinical trial. Each cohort will be fully enrolled and complete the Week 4 visit to allow for a safety review before initiating enrollment of the next dose group.

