3.2 Treatment Groups / Sample Size

The following dose groups and sample sizes are planned:

Dose Group		Vehicle	690 U	1,100 U	Σ Total
Cohort 1	N =	12	24		
Cohort 2	N =	12		24	
Total	N=	24	24	24	72

The treatment area will be preconditioned with a Dermaroller MC 905, 0.5 mm. ET-01 will be applied immediately after pre-conditioning.

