3.6 Measures to Minimize/Avoid Bias

To minimize bias, subjects will be randomly allocated to one of the three treatment groups, i.e. vehicle (group A) vs. low dose (group B) vs. high dose (group C). Neither subjects nor investigators will be aware of the treatment allocation.

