4.2 Treatment of Subjects

The study preparation or vehicle consists of a milky, white lotion of low viscosity. The drug product and diluents will be provided in kits containing 3 mL dropper bottles that contain either ET-01 or Vehicle.

The following dose groups and sample sizes are planned:

[figure not shown]
Dose Group		Vehicle	690 U	1,100 U	Σ Total
Cohort 1	N =	12	24		
Cohort 2	N =	12		24	
Total	N=	24	24	24	72

Randomization to a treatment group, i.e. ET-01 or Vehicle, will be obtained following a randomization list prepared by the Sponsor. Allocation to a dose level will be driven by sequence of enrollment.

The study medication will be applied TOPICALLY and only to subject's canthal areas. The site will be instructed to make sure no syringes or needles are present in the treatment room before study medication is brought into the room.

[figure not shown]
The treatment area is the periorbital region in the distribution of the muscles responsible for the Crow's Feet wrinkles. The muscle being treated to reduce the Crow's Feet wrinkle – the *orbicularis oculi* – is illustrated Figure 1.

Figure 1: *M. orbicularis oculi*

In general, the treatment region begins on the bony rim of the orbit, extending laterally to approximately one centimeter from the exterior edge of the hairline, 1 - 1.5 cm above and 1.5 – 2 cm below a horizontal line emanating from the lateral canthus to the hairline. This area of application is illustrated by the black outline in the picture below:

Figure 2: Treatment Area

As a guide to treatment, it is helpful to have the subject contract the orbicularis oculi muscle by asking the subject to produce a maximal smile so that the muscular extension can be visualized for that subject's treatment. In no case, however, should ET-01 ever be applied within the area circumscribed by the interior edge of the orbital rim.

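### Dose level follows order of enrolment, so the 690 U vs 1,100 U tests are fully confounded with cohort, and each dose vs pooled vehicle takes half of any cohort drift

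*Combined protocol and SAP*

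**What the plan says.** Section 4.2 separates two steps of allocation. The first is random: "Randomization to a treatment group, i.e. ET-01 or Vehicle, will be obtained following a randomization list prepared by the Sponsor". The second is not: "Allocation to a dose level will be driven by sequence of enrollment". Section 3.1 fixes the timing by requiring that each cohort be filled and "complete the Week 4 visit to allow for a safety review before initiating enrollment of the next dose group". The tables in 3.2 and 4.2 give Cohort 1 as 12 vehicle and 24 at 690 U, and Cohort 2 as 12 vehicle and 24 at 1,100 U, with the vehicle subjects added into one column of 24.

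Section 3.6 describes something else: "subjects will be randomly allocated to one of the three treatment groups", with vehicle as a single group A.

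In section 9.2.2 the primary comparisons are each active group vs vehicle on the IGA-C responder rate, by separate chi-square tests. A pooled active vs vehicle test is added, and also the dose comparison: "In addition, a separate chi-square test will be used to compare the two active drug groups". Section 9.2.3 repeats these contrasts for mean change in an ANOVA, with baseline IGA as the only possible covariate. Cohort is not named as a stratum, covariate or sensitivity analysis anywhere.

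**The concern.** No subject could have been randomised between 690 U and 1,100 U, because the second dose opens only after the first cohort has passed Week 4. Anything that changes between cohorts is therefore inseparable from dose: the investigators' scoring, site mix, experience with the Dermaroller and the long rubbing-in procedure, or subjects' expectations. An ordinary significance test presents that difference as a dose effect.

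The per-dose tests are partly exposed as well. If vehicle is pooled, half of each dose's controls come from the other cohort. Should background response rise in Cohort 2, 1,100 U looks better and 690 U looks worse, which imitates a dose response. Section 4.1 gives finding a safe and effective dose as the purpose of the study, so this bears on how the result will be read.

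**Working it through.** **Inputs.** Group sizes come from 3.2, the allocation rule from 4.2, the timing from 3.1, and two-sided alpha 0.05 from 9.2.2. Section 9.1.1 gives no response rate, effect size or power and refers only to studies LCL-206 and 207. All response rates below are therefore assumptions.

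**The plan's own figure.** 12 + 24 + 12 + 24 = 72, and 12 + 12 = 24 vehicle. Both reproduce. The power cannot be reproduced.

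**Bias.** Assume no drug effect, response rate p in Cohort 1 and p + d in Cohort 2.

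- Pooled vehicle: (12p + 12(p + d))/24 = p + d/2.
- 1,100 U minus 690 U: (p + d) − p = d.
- 1,100 U minus pooled vehicle: (p + d) − (p + d/2) = +d/2.
- 690 U minus pooled vehicle: p − (p + d/2) = −d/2.
- Pooled active minus pooled vehicle: (24p + 24(p + d))/48 − (p + d/2) = 0.
- Either dose minus its own cohort's vehicle: 0.

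**False-positive rates.** These are exact, from enumerating the binomial outcomes and applying the uncorrected chi-square test at 0.05, with no drug effect. Pooled vehicle is 12 subjects at the first rate plus 12 at the second.

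| Assumed rate, Cohort 1 / Cohort 2 | Dose vs dose | 1,100 U vs pooled vehicle | 690 U vs pooled vehicle | Pooled active vs vehicle |
|---|---|---|---|---|
| 10% / 10% | 4.7% | 4.7% | 4.7% | 4.4% |
| 5% / 10% | 7.6% | 5.1% | 3.7% | 3.9% |
| 10% / 15% | 8.3% | 6.0% | 5.8% | 4.7% |
| 10% / 20% | 16.7% | 7.6% | 8.2% | 4.8% |
| 10% / 25% | 28.8% | 9.8% | 11.7% | 4.7% |
| 10% / 30% | 43.1% | 12.4% | 16.3% | 4.6% |
| 20% / 40% | 33.3% | 11.2% | 12.6% | 4.8% |

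At very low rates the test is conservative: at 2% / 5%, dose vs dose rejects in 1.9% of trials and the per-dose tests in 0.6-1.6%.

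**Price of using concurrent vehicle only (24 vs 12).**

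- Ratio of standard errors to the pooled-vehicle comparison: √((1/24 + 1/12)/(1/24 + 1/24)) = √(0.1250/0.0833) = 1.22.
- Exact power at assumed rates of 10% vs 40%: 71% with 24 vs 24, 48% with 24 vs 12. At 10% vs 50%: 90% and 71%.
- Dose vs dose corrected through each cohort's own vehicle: √((2/24 + 2/12)/(2/24)) = 1.73 times the standard error of the direct comparison.

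**Price of stratifying pooled active vs vehicle.** The unstratified variance factor is 1/48 + 1/24 = 0.0625. Averaging two within-cohort differences, each with factor 1/24 + 1/12 = 0.125, gives (0.125 + 0.125)/4 = 0.0625. No precision is lost in the linear model.

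**The case against.** The strongest reply is about scope and size. The dose-vs-dose test is not one of the primary comparisons. The tests that are primary take only half the drift, and half of their controls are concurrent and randomised. A response needs a fall of at least 2 points on a 0-4 scale averaged over both sides, so background rates, and any drift in them, may be small. In the scenarios with 5 points of drift or less the per-dose tests reject in at most 6.0% of trials. Section 7.2 gives 7-8 months in total with 26 weeks per subject, so the cohorts are probably only one to two months apart, under the same criteria, photo scale and procedure. Section 9.5 promises a later SAP in which the matter could be handled. All of this stands, and it lowers the severity. It does not rescue the dose-vs-dose test, which is confounded at any drift and however vehicle is handled.

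Vehicle pooling is an inference: it rests on the summed total of 24, the single group A in 3.6 and the single term for vehicle in 9.2.2. It is a sound one, but 9.2.2 does not say it in words.

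A reader might go further and infer that the overall drug effect is also distorted. It is not: pooled active vs vehicle is split equally over the cohorts, and additive drift cancels. Nor do the documents show that drift exists. A reader might also infer that the blind is broken because the cohort reveals the planned dose level. No section says that sites are told the dose level, and knowing it would not show who received vehicle.

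**Conclusion.** The point holds for two sets of contrasts. The 690 U vs 1,100 U tests in 9.2.2 and 9.2.3 are non-randomised and take the whole of any cohort drift. The primary per-dose tests take half of it, in opposite directions, provided that vehicle is pooled. Separately, 3.6 contradicts 4.2 on what is randomised, and the two must be reconciled.

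The size depends wholly on assumed rates. Over cohort differences of 5 to 20 points the false-positive rate runs from 7.6% to 43.1% for dose vs dose, and from 3.7% to 16.3% for the per-dose tests. The larger figures require drifts for which the documents offer no evidence. The finding that pooled active vs vehicle is unbiased assumes additive drift and the planned group sizes. This should be fixed before unblinding, but it does not invalidate the design.

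**What to change.** 1. Label 690 U vs 1,100 U a non-randomised descriptive comparison with no inferential test, for responders and for mean change. Show it beside each dose's difference from its own cohort's vehicle.
2. State that the per-dose primary test uses pooled vehicle, and keep it as the leading result. Pre-specify as a sensitivity analysis each dose vs its concurrent vehicle (24 vs 12) with a confidence interval, and show the two vehicle subgroups side by side. State that a claim for a dose needs the two estimates to be consistent.
3. Stratify pooled active vs vehicle by cohort: a Cochran-Mantel-Haenszel test for responders and a cohort term for the pooled mean-change contrast. This makes the analysis follow the randomisation; it does not repair a bias.
4. Correct 3.6 to say that randomisation is active vs vehicle within cohort, in agreement with 4.2.

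The cost is wording in the SAP foreseen in 9.5 and a few table rows, with no new subjects or visits. The price is statistical: the concurrent-vehicle estimate has a standard error about 22% larger, and the power loss shown above would follow if it alone decided. That is why it should support the pooled-vehicle result and not replace it.
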